6.7. Prior and Concomitant Therapy

6.7.1. Concomitant Medications

Participants must be instructed not to take any medications, including over-the-counter (OTC) products, without first consulting the Investigator.

Concomitant (including immunosuppressant) medications should be administered consistently and if possible after all visit procedures and assessments, including study intervention administration and post-administration PK blood draws (if applicable).

Participants who are taking concomitant medications must be informed that on the day of the study visit, these medications are to be taken only after the study procedures and assessments are completed (if clinically appropriate) or as advised by the Investigator.

At each visit, use of any rescue therapy for worsening LN and restricted or prohibited medication beyond the protocol allowed threshold will also be assessed.

6.7.2. Prohibited Medications

Receipt of any of the following treatments leads to immediate discontinuation of study intervention:

- IV, intramuscular, or SC immunoglobulins, except anti-SARS-CoV-2 therapeutic antibodies
- Cyclophosphamide or alkylating agents (eg, chlorambucil)
- Calcineurin inhibitors (eg, cyclosporin, voclosporin, tacrolimus), mechanistic target of rapamycin inhibitors, retinoids, thalidomide, lenalidomide, or Janus kinase inhibitors.
- Transfusion with blood, packed red blood cells, platelets or treatment with plasmapheresis, plasma exchange, or Therakos® photopheresis.
- Live vaccines (the Sponsor recommends that Investigators ensure all participants are current with recommended vaccinations per local treatment standards prior to entry into the study).
- Cytokine or cytokine receptor antagonists, including but not limited to interleukin (IL)-1, IL-6, IL 17, IL-12/23, IL-23, IFN, integrin, or TNF α antagonists (except for IFN α kinoid, for which receipt at any time is exclusionary).
- Belimumab, abatacept, or eculizumab
- Other biologics used for immunosuppression or immunomodulation (eg, IFN therapy, IL-2)

- Investigational drugs
- IPP-201101 (LupuzorTM)
- B cell-depleting therapies (eg, rituximab, ocrelizumab, ofatumumab, inebilizumab, telitacicept) other than atacicept or obinutuzumab
- Receipt of systemic glucocorticoids (ie, PO, rectal, IV or IM) for more than a total of 2 weeks for any concurrent illness, including asthma, inflammatory bowel disease, or drug-induced SLE
- Atacicept
- BCG vaccination
- Obinutuzumab

6.7.3. Restricted Medications

As daxdilimab is an investigative immunomodulatory agent, non-protocol permitted changes to immune modifiers or immunosuppressants during the study are not allowed. If a participant receives one of the following after Randomization, the Investigator must notify the Sponsor/Designee Medical Monitor immediately. The Designee Medical Monitor will determine with the Sponsor if the participant may continue to receive study intervention; however, the participant would be considered a non-responder for efficacy assessments such as CRR.

- Azathioprine
- Methotrexate
- Leflunomide
- Mizoribine
- Cholestyramine
- Increase in corticosteroids (except methylprednisolone pulses) above the protocol allowed doses or duration
- Corticosteroids with a long biologic half-life (ie, dexamethasone, betamethasone)
- MMF/MPA dose above or below protocol required dose or duration

6.7.4. Permitted Therapies

6.7.4.1. Standard of Care Immunosuppressive Background Therapy

Permitted medications for SOC treatment for LN are described below. The SOC for LN will consist of the combination of MMF/MPA and corticosteroids.

6.7.4.1.1. Mycophenolate Mofetil/Mycophenolic Acid

The target dose of MMF will be 2 gm/day by mouth (or equivalent) throughout the study, where the dose is titrated to the target dose between Randomization and Week 8. For participants who are not already taking prescribed MMF prior to Randomization, the dosing of MMF will start at 500 mg BID for a total daily dose of 1 gm/day for the first week, increasing to 1 gm BID for a total daily dose of 2 gm/day for the second and subsequent weeks (ie, beginning on Day 8). An equivalent dose of MPA may be used as an alternative to MMF. All participants will take

MMF/MPA BID (ie, morning and evening), before meals (ie, on an empty stomach), with a glass of water. If a dose is missed, the participant should take the next correct dose rather than “doubling up” at the next dosing time point. A stable dose of MMF/MPA should be maintained throughout the study. Adjustments of the dose due to suboptimal response, toxicity, or intolerance are allowed if needed according to guidelines described below. A maximum dose of 3.0 gm/day is allowed up to Week 24 for participants with suboptimal response between Weeks 8 and 24 with a reduction to \leq 2.0 gm/day by Week 32. The dose of MMF must be stable from Week 40 to Week 52.

After Week 52, MMF dose should be \leq 2 gm/day. If MMF dose $>$ 2 gm/day at Week 52, taper to \leq 2 gm/day is recommended by Week 60. The dose of MMF must be stable from Week 92 to [REDACTED].

It is not mandatory for a participant to receive 2 gm/day of MMF (or equivalent) if local treatment standards dictate a lower dose to be given (eg, for constitutionally small participants). The minimum dose of MMF is 1.0 gm/day (or equivalent) after Week 8 through [REDACTED]. Participants who do not tolerate the minimum MMF dose (or equivalent) will be considered non-responders for responder analyses (such as CRR) but will be allowed to continue to receive study intervention. However, if MMF/MPA is discontinued and a different immunosuppressant is started, the study intervention will be discontinued. A decrease below the minimum dose or withholding MMF/MPA for 14 days or less for MMF/MPA related side effects, such as gastrointestinal side effects, cytopenias or infection is acceptable at any time throughout the study. If MMF/MPA must be withheld or decreased below the minimum dose for more than 14 days, the participant will be considered a non-responder for responder analyses (such as CRR) but may continue to receive study intervention (this will not be considered as non-compliance or a protocol deviation because the withdrawal of MMF/MPA is for safety reasons).

The use of IV forms of mycophenolate is prohibited.

Initial adjustment of MMF/MPA dose to achieve or maintain the target dose (Randomization through Week 8)

- Participants who are receiving MMF/MPA at a dose of 2 gm/day (or equivalent) at Week 0 (Day 1) will continue this dose without interruption.
- Participants who are not taking MMF/MPA at Week 0 (Day 1) or participants who are taking less than 2 gm/day (or equivalent), the dose will be titrated up with the goal of achieving a dose of 2 gm/day (or the therapeutic target dose if local treatment standards dictate a lower dose) by Week 1 (Day 8) (but not later than Week 8 (Day 57), if dose escalation is limited by intolerance).

Titration of MMF/MPA should follow accepted local practice guidelines, including appropriate laboratory monitoring for toxicity.

- Participants who at Week 0 (Day 1) are taking MMF doses $>$ 2 gm/day will have their dose reduced to 2 gm/day by Week 8 (Day 57) unless they meet criteria for suboptimal response (see below for suboptimal response).

MMF/MPA dose between Week 8 and 24

The dose of MMF/MPA will be kept stable from Week 8 through Week 24 unless dose escalation to a maximum of 3 gm/day is necessary for suboptimal response (defined below) or a dose reduction is necessary to manage toxicity or intolerance.

Criteria for suboptimal response:

A suboptimal response is defined by UPCR values shown below **at two independent measurements taken at least 2 weeks apart:**

- Spot UPCR > 3 mg/mg and
- Spot UPCR < 15% decrease compared to baseline spot UPCR

If a participant meets the criteria at or after Week 8, the dose may be escalated or kept above 2 gm/day. After initial confirmation of suboptimal response, MMF/MPA can be increased up to 3 gm/day (or equivalent) until Week 16 without re-testing for the suboptimal response criteria. The dose of MMF/MPA must be kept stable from Week 16 unless dose reduction is necessary for intolerance or MMF/MPA-related AEs. A temporary decrease below the minimum dose or withholding MMF/MPA for 14 days or less for MMF related side effects, such as gastrointestinal side effects, for cytopenias or infection is acceptable.

MMF/MPA dose between Week 24 and Week 52:

For participants who are taking > 2 gm/day of MMF (or MPA equivalent) at Week 24, the dose of MMF/MPA must be decreased to a maximum dose of 2 gm/day (or equivalent) by Week 32. **The dose of MMF/MPA must be stable from Week 40 through Week 52 (unless a dose reduction is necessary to manage toxicity or intolerance).**

MMF/MPA dose from Week 52 to [REDACTED]

The target dose of MMF/MPA will be \leq 2 gm/day. If the MMF/MPA dose is $>$ 2 gm/day at Week 52, it should be tapered to \leq 2 gm/day by Week 60.

MMF/MPA dose must not be changed from Week 92 to [REDACTED].

6.7.4.1.2. Corticosteroids

Initial corticosteroid treatment to control LN and SLE:

Participants may enter the study taking daily OCS at a maximum dose of 0.5 mg/kg/day of prednisone-equivalent, not to exceed 40 mg/day, and must be on a stable dose for at least 10 days prior to Randomization. In addition, participants will receive IV methylprednisolone pulse 500 mg on the day of Randomization, prior to receiving the study intervention, unless they received a methylprednisolone pulse of \geq 500 mg within 10 days prior to Randomization. Participants may also receive one additional (optional) dose of IV methylprednisolone pulse (\leq 500 mg) for renal or extra-renal disease activity after the Week 0 (Day 1) Visit up to and including the Week 8 Visit. Methylprednisolone pulse can be divided and administered on two consecutive days, but the cumulative dose must not exceed 500 mg.

Steroid tapering during the study

Oral corticosteroid dose tapering is required during the study with the goal of fractionally reduce OCS to a prednisone-equivalent dose of \leq 7.5 mg/day by Week 12 and prednisone-equivalent dose of \leq 2.5 mg/day by Week 24. The rate of tapering is at the discretion of the Investigator; a recommended tapering schedule is provided below.

Table 9 Recommended Oral Prednisone Tapering Schedule

Starting Prednisone Dose (mg/day)	10 mg/day	20 mg/day	30 mg/day	40 mg/day
Week 2 (Day 15)	10	15	25	35
Week 4 (Day 29)	10	15	25	30
Week 6 (Day 43)	7.5	10	20	25
Week 8 (Day 57)	7.5	10	15	20
Week 10 (Day 71)	5	7.5	10	15
Week 12 (Day 85)	5	7.5	7.5	7.5
Week 16 (Day 113)	2.5	5	5	5
Week 20 (Day 141)	2.5	2.5	2.5	2.5
Week 24 (Day 169)	2.5	2.5	2.5	2.5

If participants experience an increase in SLE disease activity upon tapering of OCS, their dose may be returned to a dose equal to or less than the dose prior to the taper. The return to the pre-taper dose will not be considered an OCS “burst and taper”. The pre-taper dose for various periods is defined as follows:

- Week 0 to Week 12: dose at Randomization
- After Week 12 to Week 24: the Week 12 dose
- After Week 24 to Week 44: the Week 24 dose

Participants unable to taper OCS to \leq 15 mg/day at Week 12 or \leq 10 mg/day at Week 24 will be discontinued from study intervention treatment (See Section 7.1.1). However, participants who exceed the maximum daily OCS dose at the Week 12 or Week 24 Visits may continue to receive study intervention if the current dose is part of a protocol allowed temporary OCS dose (eg, burst and taper) increase. Participants who cannot be returned to their pre-increase dose within 14 days from the start of burst will have their study intervention discontinued at the next visit.

Participants who prematurely stop dosing prior to Week 52 will be followed for regularly scheduled visits through Week 52 unless participants withdraw consent of trial participation (See Section 7.1.3) or are lost to follow-up (See Section 7.2). Participants should be followed to assess AE/SAEs for at least 12 weeks after the last study intervention administration, approximately 4, 8, and 12 weeks after the last study intervention dose, unless the participant withdraws consent.

Participants who prematurely stop dosing after Week 52 but remain in the study will complete the EOT Visit and the SFU Period, unless the participant withdraws consent. Participants will not automatically be removed from the trial if any administration of study intervention is missed

Investigators will not be required, but may continue, to taper OCS dose beyond the target of 2.5 mg/day up to Week 40, including discontinuation of OCS. **Steroid tapering will not be permitted from Week 40 to Week 52.**

Continued tapering of OCS is recommended for all participants after the Week 52 Visit with the goal of achieving discontinuation (ie, 0 mg) by Week 76. Due to variability in participant responses to OCS treatment and tolerability of taper, Investigators will have flexibility of when the OCS dose is reduced at each visit. No change in OCS dose will be allowed from Week 92 to [REDACTED]

Steroid “burst and taper”

A steroid burst is defined as one of the following:

- OCS increase up to a maximum daily dose of 0.5 mg/kg/day (maximum 40 mg/day) prednisone-equivalent dose for up to a total of 14 days which must be fully administered and tapered to less than or equal to the pre-burst starting dose by the end of the 14th day. Any course of OCS burst must not extend beyond Week 40, regardless of when the course was started.

OR

- A maximum of 1 instance of intra-articular, tendon sheath or bursal injections (for a total dose of methylprednisolone \leq 80 mg or equivalent) can be given. Participants who receive any intraarticular/tendon sheath/bursal injections should not receive OCS burst (and vice versa).

Steroid burst is allowed as follows:

- **From Randomization to Week 40:** One burst and taper of corticosteroids for increased SLE disease activity or for non-SLE activity is allowed.

Participants who receive more than one steroid “burst and taper” or who violate the above criterion may continue to receive study intervention after approval by Sponsor/Designee Medical Monitor, but will be considered non-responders for subsequent responder analyses (such as CRR) to be further described in the SAP, regardless of whether the OCS “burst” was administered for increased SLE activity or non-SLE causes.

- **Increase in corticosteroids from Week 40 to Week 52:** No increase in OCS, or the use of IV or intra-articular, tendon sheath or bursal injections is allowed from Week 40 until the Week 52 assessment.
- One burst and taper will be allowed between Week 52 and Week 92.

Increase in corticosteroids for the prevention of adrenal insufficiency

For a severe illness, surgery, or symptoms of adrenal insufficiency, if clinically warranted, the following can be used, in addition to the “burst and taper” described above from Randomization to Week 40 without the participant being considered a non-responder:

- Oral or IV hydrocortisone up to 100 mg every 8 hours on the first day followed by half of the previous dose for 2 days before returning to their usual dose **OR**

- Participants who are taking ≤ 7.5 mg/day prednisone or equivalent will be allowed to receive up to an additional 7.5 mg/day to a total of 15 mg/day oral prednisone or equivalent for a total of up to 14 days.

Participants who receive either of these corticosteroid regimens for the prevention of adrenal insufficiency between Week 40 and Week 52 will be considered as a non-responder for the analyses at Week 52.

6.7.5. Other Concomitant Medications

Medications other than the SOC immunosuppressive background therapy described above, which are considered necessary for the participant's safety and wellbeing, may be given at the discretion of the Investigator and recorded in the appropriate sections of the electronic Case Record Form (eCRF). Participants should not start naturopathic, herbal, ayurvedic remedies, nutritional/dietary supplements, vitamins, and/or minerals without discussing with the Investigator.

6.7.5.1. Anti-Hypertensive Agents and HMG-CoA Reductase Inhibitors (Statins)

Routine use of Angiotensin-Converting Enzyme Inhibitor (ACEI) or Angiotensin II Receptor Blockers (ARB) is recommended for all participants unless contraindicated. Use of anti-proteinuric agents are allowed during the study if they had been started at least 10 days prior to the assessment of the second screening 24-hour UPCR sample (ie, the first sample for 24-hour UPCR is collected at the start of the Screening process and the second sample is collected within 14 days prior to the expected date of Randomization). The dose may be adjusted to optimize anti-hypertensive effects or to reduce ACEI/ARB-related side effects up to Week 4. The dose must be kept stable from Week 4 through [REDACTED]. Dose reductions are allowed only to reduce ACEI/ARB-related side effects such as hypotension, increase in creatinine, or cough. If cough develops, ACEI may be changed to ARB. Changes in other classes of anti-hypertensive agents (eg, calcium channel receptor blockers, beta-adrenergic receptor blockers, alpha-adrenergic receptor blockers) are allowed as clinically indicated to optimize blood pressure.

Statins must be kept at stable doses after Day 1. Decreases in the dose are allowed only to reduce statin-related side effects.

Cholestyramine must be discontinued prior to the day of Randomization.

6.7.5.2. Sodium-Glucose Cotransport 2 Inhibitors

Use of Sodium-Glucose Cotransport 2 (SGLT2) inhibitors is allowed during the study if they had been initiated to treat Type 2 diabetes mellitus only. No increase in the dose of or initiation of SGLT2 inhibitors should be made between signing the ICF and Randomization. For participants receiving SGLT2 inhibitors, the dose must remain stable from Randomization through [REDACTED] and may be reduced only for reasons of toxicity but not for efficacy.

6.7.5.3. Anti-Malarial Agents

The dose of anti-malarial agents should remain stable throughout the study except where a dose reduction is necessary to manage anti-malarial-related AEs. Any anti-malarial-related abnormality should be managed according to local standards. Discontinuation of antimalarials is

allowed, if necessary, to manage anti-malarial-related AEs. The participant may remain in the study even if anti-malarial agents are stopped.

All participants who have been taking anti-malarial therapy within 12 months of signing the ICF must have an eye exam by a qualified professional either within 12 months prior to signing the ICF or within 12 weeks after signing the ICF. Anti-malarial-related abnormalities should be managed according to local standards. Anti-malarial-related abnormalities do not exclude participants if they meet all other eligibility criteria. If an eye exam is not performed within the protocol specified timeframe, it will be considered as a protocol deviation.

6.7.5.4. Non-Steroidal Anti-inflammatory Drugs

No increase in the dose of or initiation of a new prescription non-steroidal anti-inflammatory drugs (NSAID) should be made between signing the ICF and Randomization. For participants receiving NSAIDs, concomitant histamine H₂-receptor antagonists should be considered according to local practice and in concordance with considerations in the mycophenolate label.

The dose of prescription NSAIDs must remain stable from Randomization through [REDACTED] and may be reduced only for reasons of toxicity but not for efficacy. Prescription NSAIDs should not be administered with other NSAIDs (including OTC NSAIDs) except for low-dose aspirin (\leq 325 mg/day).

Non-prescription NSAIDs

- NSAIDs for analgesic purposes that never exceed label-approved doses of NSAIDs may be used for pain as required, based on Investigator judgement for up to 1 week at a time.
- Low-dose aspirin (maximum of 325 mg/day) for cardioprotection is permitted.

6.7.5.5. Acetaminophen (Paracetamol)

Normal release (not extended release) acetaminophen/paracetamol may be used for pain as required.

6.7.5.6. Narcotic Analgesics

Narcotic analgesics may be used during the study as clinically indicated.

6.7.5.7. Topical Therapy

Concurrent use of topical therapy for cutaneous lupus erythematosus (eg, topical corticosteroids, topical immunosuppressants) is permitted. During the study, topical therapy may be reduced or discontinued based on clinical manifestations and Investigator discretion. Should cutaneous skin manifestations reoccur, the same topical therapy may be resumed at same dose as was being used at the time of Randomization.

It is encouraged that no new dermatologic preparations be initiated for the duration of the study. Participants should use sunscreen (list as concomitant medication for SLE) and avoid sun exposure for the duration of the study.

6.7.6. **Rescue Medicine**

The study site will supply rescue medication at any time during the study. Although the use of rescue medications is allowable, the use of rescue medications should be delayed, if possible. The date and time of rescue medication administration as well as the name and dosage regimen of the rescue medication must be recorded.

Rescue therapy for worsening LN may be administered at the discretion of Investigators as clinically indicated. Rescue therapy includes the initiation of any new treatment for lupus or LN or an increase from baseline in the SOC background therapy (MMF/MPA or corticosteroids). For any rescue medications, study intervention may be continued after discussion with and approval by the Horizon Medical Monitor. However, if the participant receives a prohibited medication as a rescue, study intervention will be discontinued. Participants who receive rescue therapy will be considered treatment failures for subsequent endpoint analyses (such as CRR).

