[REDACTED] Under exceptional circumstances such as delayed laboratory results, drug washout, or the impact of COVID-19, the Screening Period may be increased by 2 weeks, upon approval by the Medical Monitor. In general, re-screening of participants may occur only in consultation with and approval by the Medical Monitor. The trial will be conducted on an outpatient basis. For all administrations, study intervention will be administered by site staff in the clinic and the participant will be observed for at least 60 minutes after the first three doses as well as at [REDACTED]

[REDACTED] Participants who prematurely stop dosing prior to Week 52 will be followed for regularly scheduled visits through Week 52 unless participants withdraw consent of trial participation (See Section 7.1.3) or are lost to follow-up (See Section 7.2). Participants should be followed to assess AE/SAEs for at least 12 weeks after the last study intervention administration, approximately 4, 8, and 12 weeks after the last study intervention dose, unless the participant withdraws consent. Participants who prematurely stop dosing after Week 52 but remain in the study will complete the End-of-Treatment (EOT) Visit and the SFU Period, unless the participant withdraws consent. Participants will not automatically be removed from the trial if any administration of study intervention is missed.

Rescue therapy for worsening LN may be administered at the discretion of Investigators as clinically indicated. Rescue therapy includes the initiation of any new treatment for lupus or lupus nephritis or an increase from baseline in the standard-of-care background therapy (MMF/MPA, or corticosteroids). For any rescue medications, study intervention may be continued after discussion with and approval by the Horizon Medical Monitor. However, if the participant receives a prohibited medication as a rescue, study intervention will be discontinued (See Section 6.7.2). Participants who receive rescue therapy will be considered treatment failures for subsequent endpoint analyses (such as CRR).

The primary assessment of the efficacy endpoints will be performed at [REDACTED]. The

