7.1.1. Discontinuation of Study Intervention

Blinded study intervention will be discontinued in participants who meet pre-defined criteria for worsening LN or SLE.

Criteria for discontinuing study intervention for worsening LN or SLE (at any time):

- > 30% decrease in eGFR compared to baseline due to LN **and** eGFR < 60 mL/min/1.73 m² (compared to the average of the previous two visits, not explained by change in comorbidities or concomitant medications. A decrease in eGFR must be confirmed on at least two independent samples at least 5 days apart after non-SLE causes have been corrected or excluded) **OR**
- Increase in renal or extra-renal lupus activity requiring prohibited systemic immunosuppressive treatment (eg, cyclophosphamide, rituximab, belimumab) **OR**
- Receipt > 1 methylprednisolone pulse after the day of Randomization **OR**
- Receipt of any methylprednisolone pulse after Week 8 **OR**
- The study intervention will be discontinued if MMF is discontinued, and another immunosuppressant is initiated

Criteria for discontinuing study intervention for worsening LN or SLE at Week 12 and Week 24:

- eGFR < 75% of baseline and < 60 mL/min/1.73 m² (compared to the average of the previous two visits, not explained by change in comorbidities or concomitant medications. A decrease in eGFR must be confirmed on at least two independent samples at least 5 days apart after non-SLE causes have been corrected or excluded) **OR**
- Nephrotic range UPCR (confirmed by a second measurement at least two weeks after the first measurement):
 - Participants with 24-hour UPCR \leq 3 mg/mg at baseline will be withdrawn if 24-hour UPCR increases by > 50% from baseline to > 3.5 mg/mg
 - Participants with 24-hour UPCR > 3 mg/mg at baseline will be withdrawn if 24-hour UPCR **at Week 24** > 3.5 mg/mg and there is < 50% improvement from baseline

OR

- Inability to adhere to corticosteroids requirements:
 - Inability to reduce OCS to \leq 15 mg/day prednisone-equivalent at Week 12
 - Inability to reduce OCS to \leq 10 mg/day prednisone-equivalent by Week 24

Participants who exceed the maximum daily OCS dose at the Week 12 or Week 24 Visits may continue to receive study intervention if the current dose is part of a temporary increase in OCS dose (eg, protocol allowed burst and taper). Participants who cannot be returned to their pre-increase dose within 14 days from the start of the increase will have their study intervention discontinued at the next visit.

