Participants who prematurely stop dosing prior to Week 52 will be followed for regularly scheduled visits through Week 52 unless participants withdraw consent of trial participation (See Section 7.1.3) or are lost to follow-up (See Section 7.2). Participants should be followed to assess AE/SAEs for at least 12 weeks after the last study intervention administration, approximately 4, 8, and 12 weeks after the last study intervention dose, unless the participant withdraws consent.

Participants who prematurely stop dosing after Week 52 but remain in the study will be complete the EOT Visit and the SFU Period, unless the participant withdraws consent. Participants will not automatically be removed from the trial if any administration of study intervention is missed.

Early discontinuation of study intervention for reasons other than lack of efficacy

An individual participant will not receive any further study intervention if any of the following occur in the participant:

- Receipt of Prohibited Medications (See Section 6.7.2).
- A Common Terminology for Adverse Events (CTCAE v5.0 dated 27 NOV 2017) Grade 3 or higher allergic reaction to the study intervention.
- A CTCAE Grade 3 or higher infection considered related to the study intervention.
- Other AE that contraindicates further dosing in the opinion of the Investigator and/or the Sponsor, or Medical Monitor.

- Withdrawal of consent from further treatment with study intervention.
- Participant is determined to have met one or more of the exclusion criteria or failed to meet all the inclusion criteria for study participation and there is a potential safety risk associated with continuation identified upon consultation with the Medical Monitor.
- Pregnancy or a decision to become pregnant.
- Any of the following liver function abnormalities:
 - alanine aminotransferase (ALT) or aspartate aminotransferase (AST) $\geq 8 \times$ ULN.
 - ALT or AST $\geq 5 \times$ ULN for more than 2 weeks.
 - ALT or AST $\geq 3 \times$ ULN and total bilirubin $\geq 2 \times$ ULN.
 - ALT or AST $\geq 3 \times$ ULN with the appearance of fatigue, nausea, vomiting, right upper quadrant pain or tenderness, fever, rash, and/or eosinophilia ($\geq 5\%$).

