8. STUDY ASSESSMENTS AND PROCEDURES

Description of Study Procedures and Assessments

Trial procedures and their timepoints are summarized in the SoA (see Section 1.3). Protocol waivers or exemptions are not allowed.

Adherence to the trial design requirements, including those specified in the SoA, is essential and required for trial conduct.

All Screening evaluations must be completed and reviewed to confirm that potential participants meet all eligibility criteria.

The Investigator will maintain a Screening Log to record details of all participants screened and to confirm eligibility or record reasons for screening failure, as applicable.

Procedures conducted as part of the participant's routine clinical management and obtained before signing of the ICF may be utilized for screening or baseline purposes provided the procedures met the protocol-specified criteria and were performed within the timeframe defined in the SoA.

In the event of a significant trial-continuity issue (eg, caused by a pandemic), alternate strategies for participant visits, assessments, medication distribution, and monitoring may be implemented by the Sponsor or the Investigator, as per local health authority/ethics requirements.

Safety, laboratory, and/or analyte results that could unblind the trial will not be reported to investigative sites or other blinded personnel.

Repeat or unscheduled samples may be taken for safety reasons or for technical issues with the samples.

All procedures and assessments and laboratory tests (unless otherwise specified) will be done prior to administration of study intervention.

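### The rescue rule lets the Medical Monitor approve continued dosing after a methylprednisolone pulse that Section 7.1.1 makes a mandatory stop

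*Protocol*

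**What the plan says.** **Rescue rule (Protocol 6.7.6, repeated in 4.1 and the synopsis).** Rescue for worsening LN is at the Investigator's discretion. It covers any new lupus or LN treatment and any rise from baseline in MMF/MPA or corticosteroids. On dosing afterwards: "For any rescue medications, study intervention may be continued after discussion with and approval by the Horizon Medical Monitor". One exception follows: "However, if the participant receives a prohibited medication as a rescue, study intervention will be discontinued". Section 4.1 and the synopsis point that exception to 6.7.2.

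**Stopping rule (Protocol 7.1.1).** Blinded study intervention is to be discontinued when a pre-defined criterion for worsening LN or SLE is met. Two criteria, applying at any time, concern pulses: "Receipt > 1 methylprednisolone pulse after the day of Randomization" and "Receipt of any methylprednisolone pulse after Week 8". A separate list in the same section, for reasons other than lack of efficacy, includes "Receipt of Prohibited Medications (See Section 6.7.2)".

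**Related text.** The only systemic glucocorticoid entry in 6.7.2 is use "for more than a total of 2 weeks for any concurrent illness, including asthma, inflammatory bowel disease, or drug-induced SLE". Section 6.7.3 lists drug changes on which the Medical Monitor and Sponsor decide about continuation, and it leaves methylprednisolone pulses out of its corticosteroid entry. Section 6.7.4.1.2 allows one optional extra pulse of up to 500 mg, no later than the Week 8 Visit. Section 8 adds: "Protocol waivers or exemptions are not allowed".

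**The concern.** A pulse given at, say, Week 20 for worsening LN is rescue under 6.7.6, so dosing may go on if the Medical Monitor agrees. Under 7.1.1 the same pulse ends dosing with no discretion. Neither section refers to the other on this point, and no order of precedence is stated. A site that looks up rescue where rescue is described would find only the permissive rule.

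If continuation is approved, four things depend on which section was followed:

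- whether a participant who has met a stopping criterion for worsening disease keeps receiving blinded drug;
- the treatment-discontinuation counts (SAP 4.5);
- Stage II dosing and membership of the Stage II Analysis Set (SAP 4.4.4);
- whether post-rescue data in the treatment-policy supplementary analyses (SAP 4.8.1.6 and 4.8.2.3) were collected on or off drug.

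A pulse given for a reason other than worsening LN falls under 7.1.1 alone and is not part of this point.

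**Working it through.** The plan states no figure to reproduce. The check compares the texts and then counts the doses at stake.

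**1. The two rules side by side, for a pulse given as rescue for worsening LN**

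| Event | 6.7.6, 4.1, synopsis | 7.1.1 |
|---|---|---|
| First pulse after Day 1, up to Week 8 | May continue with approval | No pulse criterion met |
| Second pulse after the day of Randomization | May continue with approval | Must stop |
| Any pulse after Week 8 | May continue with approval | Must stop |

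**2. Does the exception in the rescue rule close the gap?** No. It covers prohibited medications only. The 6.7.2 glucocorticoid entry concerns more than 2 weeks of treatment for a concurrent illness, which does not describe a pulse for LN. Section 7.1.1 lists prohibited medications and pulses as separate stops, so the exception carries over only one of them.

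**3. Is there discretion inside 7.1.1?** Not for pulses. Where that section wants flexibility it writes it out: the allowance for a temporary OCS increase at Weeks 12 and 24.

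**4. Effect on the analyses**

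- CRR, ORR and sustained OCS reduction: no change. Rescue and treatment discontinuation both count as failure.
- Main eGFR analysis: no change. Data after rescue are excluded either way.
- Supplementary treatment-policy analyses: all observed data are used, on drug if dosing continued and off drug if it stopped.
- Stage II: "Participants who prematurely stop dosing prior to Week 52 will be followed for regularly scheduled visits through Week 52", without further doses. Such a participant would not enter the Stage II Analysis Set, which needs at least one Stage II dose. A participant allowed to continue could enter it.

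**5. Doses decided by the choice of section**

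Inputs: 19 administrations in total (synopsis); last dose at Week 100 (synopsis); 15 first-year visits, numbered 2 to 16 (Table 3); pre-dose PK samples at Weeks 2, 4, 8, 12, 16, 20, 24, 36, 48, 52, 64, 76, 88 and 100 (8.4). Section 8.4 also lists Week 104, which is the end-of-treatment visit and not a dose. The study-week row is redacted, so the schedule is an assumption: Weeks 0, 2 and 4, then every 4 weeks from Week 8 to Week 52, then Weeks 64, 76, 88 and 100.

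- First-year doses: 3 + [(52 − 8)/4 + 1] = 3 + 12 = 15, matching the 15 visits.
- Stage II doses: (100 − 64)/12 + 1 = 4.
- Total: 15 + 4 = 19, matching the stated number.

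| Rescue pulse falls between | Doses remaining | Share of 19 |
|---|---|---|
| Week 8 and Week 12 doses | [(52 − 12)/4 + 1] + 4 = 15 | 79% |
| Week 48 and Week 52 doses | 1 + 4 = 5 | 26% |
| Week 52 and Week 64 doses | 4 | 21% |
| Week 88 and Week 100 doses | 1 | 5% |

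**The case against.** The strongest reply is that both rules can be obeyed at once. Section 6.7.6 grants a permission that depends on approval, and a Medical Monitor who withholds approval complies with both. A mandatory, event-specific rule in the dedicated stopping section should override a general permission. Sections 6.7.3 and 6.7.4.1.2 point the same way, and Section 8 rules out waivers. On this view only a cross-reference is missing, and the route to error is narrow because no site can continue dosing on its own.

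Much of this stands. Section 7.1.1 is very probably meant to govern, and the approval step is a real if partial safeguard. But that shows which text to correct; it does not make the texts agree. The rescue rule is stated three times, covers all rescue, and names a single exception that is not this one. An approval given under 6.7.6 follows the protocol's own words, so the ban on waivers does not catch it. Continuation by Medical Monitor approval is also a normal route in this protocol: 6.7.4.1.2 uses it for more than one steroid burst.

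It is also fair to say that the consequences are limited. The pulse criteria concern worsening disease, and the toxicity stops are listed separately, so this gap bypasses none of them. Discontinuation counts are descriptive, as is the final analysis of participants without PRR or CRR (SAP 4.15). The Stage II assignment tables are redacted, so a separate rule there for rescued participants cannot be excluded. The dose shares show only how many doses remain at chosen dates; they say nothing about how often the situation arises.

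**Conclusion.** The protocol is wrong as written on this point. For a pulse given as rescue for worsening LN, 6.7.6, 4.1 and the synopsis authorise an approval that 7.1.1 forbids. No main efficacy result changes. Any effect requires that continuation is actually approved. It then falls on exposure after a stopping criterion is met, on disposition and Stage II membership, and on the supplementary analyses. Per affected participant, between 79% and 5% of the 19 doses depend on the section followed, for the pulse timings shown and on the reconstructed schedule. The documents give no pulse rate, so no number of participants can be stated. The point is worth correcting because continued dosing of a participant with worsening LN should not depend on which section was read.

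**What to change.** In 6.7.6, 4.1 and the synopsis, widen the exception to say that dosing stops when the rescue is a prohibited medication (6.7.2) or when any stopping criterion in 7.1.1 is met. The wider clause changes nothing the sponsor appears to intend, because the 7.1.1 stops are already mandatory.

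The cost is one clause in three places, by clarification letter or at the next amendment. It adds no participants, visits or data collection.
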